5.1 BT Run-in

All subjects will complete an initial 4-week BT program in which they will attend weekly individual weight loss sessions of 20-30 minutes led by practitioners with training and experience in the delivery of BT (e.g., registered dietitians (RDs), NPs, psychologists). Subjects will be instructed to consume a self-selected diet of 1200-1500 kcal/day (for those who weigh < 250 lb) or 1500-1800 kcal/day (for those who weigh \geq 250 lb) and be asked to begin to gradually increase their physical activity levels. Subjects will be counseled on how to consume a well-balanced diet and will be taught to use calorie counting and self-monitoring (e.g.,

Myfitnesspal, paper diaries) to meet their goals.

5.2 BT Intervention

Following randomization, all subjects will continue to attend individual (20-30 minute) BT sessions weekly for 12 weeks, then every other week until week 24 (total of 18 sessions). Subjects will be instructed to continue to follow their calorie goal and to engage in low-to-moderate intensity physical activity (e.g., walking), gradually building to a goal of ≥ 180 minutes per week (spread across 5 days) by week 24. They will be provided a curriculum on behavioral weight control, based on prior studies,^{80, 81} that includes self-monitoring, stimulus control, goal-setting, problem-solving, cognitive restructuring, and relapse prevention. Subjects will continue to monitor their food intake, physical activity, and weight online (e.g., Myfitnesspal) unless they prefer paper diaries. Subjects who miss a treatment visit will be contacted by the research coordinator and invited to complete a make-up session with study staff.

Initially, BT sessions were primarily provided in-person (make-up sessions were conducted in person or by phone). Consistent with University policy, all BT sessions will be provided by telehealth (phone or secure teleconferencing system) while recommendations to maintain remote activities due to COVID-19 remain in place.

BT interventionists will include RDs, NPs, and psychologists who are experienced in delivering lifestyle modification. Before beginning the study, interventionists will receive a 2-hour overview of obesity and its behavioral management, followed by ongoing weekly group clinical supervision. The PI will observe each provider delivering a treatment session at least once every 6 months to provide individualized feedback and ensure protocol adherence.

5.3 Medication and Placebo Interventions

In addition to attending BT sessions, non-responders will take a once daily study medication (phentermine or placebo) beginning at the randomization visit. The study medication will be provided in capsule form, and participants will be encouraged to take the medication in the morning upon awakening. Subjects will receive a 30-day supply of the study medication on each of 6 occasions. Phentermine will be provided as 8.0mg/d for the first 2 weeks to facilitate its acceptance to participants. The dose will be increased at week 2 to 15 mg/d (or further placebo) in all participants. Phentermine (or placebo) will be down-titrated (back to 8.0mg/d) or terminated in patients who report that they cannot tolerate the medication after a prolonged effort to do so. Down-titration will be managed in a blinded manner by Penn's Investigational Drug Service (IDS), in response to notification from the principal investigator (or study co-investigators) of patients' complaints of symptoms. (With IDS, we successfully used this titration method in prior randomized placebo-controlled trials of sibutramine for weight loss⁸² and of the addition for 12 weeks of phentermine or placebo to liraglutide 3.0 mg.⁸³) Participants in whom phentermine (or placebo) is terminated will continue to receive BT for the remainder of the 24-week treatment period.

5.4 Preparation and Packaging of Study Medications

Phentermine (and placebo) will be purchased and then packaged in blinded capsules by Penn's Investigational Drug Service (IDS). IDS has prepared medications before for our Center in this manner, including the preparation of phentermine and placebo for a recent 12-week trial.⁸³ IDS will store all phentermine-placebo at the hospital, to be picked up on a weekly or every-other-week basis by study coordinators and distributed to study patients.

5.5 Medication Storage

Drug supplies will be kept in a secured enclosure with limited access, both at the IDS where the medication is packaged, and at the Center for Weight and Eating Disorders (the Center), where it will be dispensed to subjects. The PI and research coordinator will ensure the availability of proper storage conditions at the Center. We will maintain adequate drug inventory and security at all times. Unused medication(s) will be stored separately from used trial medication(s). The PI will take appropriate precautions to prevent theft or diversion of the study drug.

5.6 *Blinding*

A master file of subject assignments will be kept by the pharmacists at IDS. Once a subject is randomized, the research team will receive a medication blister pack or container labeled with the subject identification number from IDS. The research team and the subject will be blinded and will not know the investigational product contained in the container. The blind may be broken in the case of an emergency. To request unblinding, the PI or a member of the study team who has been authorized by the PI will contact IDS to receive the relevant subject(s)’ information.

5.7 *Administration and Accountability*

A record of product administration will be maintained by IDS and in the subject’s file by the study team, including the medication identification number, date of distribution, and date that the product was returned by the subject. A standard form will be utilized to document this information throughout the study period.

5.8 *Subject Compliance Monitoring*

BT interventionists will briefly review the subject’s medication adherence at each visit, determining the number of days the medication was used each week and identifying reasons for missed doses. The number of doses of medication taken each week will be tracked. Interventionists will help subjects to problem solve barriers to adherence to the medication regimen and will refer subjects to the study physician or NP on an as needed basis. Subjects will be asked to return used medication containers, which will allow the study team to obtain an objective measure of the subject’s adherence to the medication regimen.

6 Study Procedures

Table 1. Proposed timeline of study visits and procedures for non-responders who lose < 2% and responders who lose $\geq 2\%$ of initial weight after 4 weeks of intensive behavioral treatment (BT).

7

CONFIDENTIAL

16

7.1 Screening Procedures

Phone screens will be conducted by trained staff to assess preliminary eligibility. Individuals who appear to be eligible will be invited for an in-person screening visit that will include a behavioral evaluation conducted by a psychologist (including the PI). Prior to their screening visit, applicants will complete questionnaires that are administered as part of standard clinical practice at the Center for Weight and Eating Disorders: the Beck Depression Inventory-II (BDI-II)⁸⁴ to assess symptoms of depression; and the Weight and Lifestyle Inventory (WALI)⁸⁵ to provide information about the individual's weight history, disordered eating behaviors, and other health behaviors (e.g., food intake, alcohol consumption).

The in-person interview will be conducted by a psychologist, who will obtain informed consent and evaluate subjects' behavioral eligibility (i.e., willingness and appropriateness to participate). This will include our assessment of the applicant's mood (as measured by interview and the BDI-II) and suicidality (including history of suicidal ideation and behavior, as assessed at screening by interview and the Columbia-Suicide Severity Rating Scale⁸⁶). Subjects who remain interested and pass this portion of the assessment will provide a medical history and physical examination to determine medical eligibility. Persons who continue to remain eligible will proceed to have a fasting blood test to determine that final eligibility criteria are met. Safety screening labs will include a comprehensive metabolic panel (CMP) and lipid panel, and a urine pregnancy test (for females of child-bearing age). An electrocardiogram (EKG) also will be performed to confirm medical eligibility prior to any participant's enrollment in the randomized trial. We anticipate completing 180 in-person screenings to obtain an initial sample of 150 subjects.

7.2 Randomization Visit

Following the 4-week BT run-in, subjects will attend a randomization visit (week 0, described to subjects as a "progress assessment visit") at which their percent weight loss from the start of the BT program (week -4) will be calculated. Subjects who have lost $\geq 2\%$ of initial weight at this time will be categorized as early responders and will not be eligible for participation in the randomized trial. These subjects will be offered an additional 24 weeks of BT but will not receive a study medication.

Subjects who have lost $<2\%$ of initial weight at the randomization visit will be categorized as early non-responders. Trained research staff will review with randomization-eligible subjects information related to the study medication, including possible risks and benefits, and will confirm applicants' willingness to participate prior to enrolling them in the randomized phase of the trial. Interested subjects will then have their eligibility confirmed by trained research staff, including completion of a urine pregnancy test. Non-responders who remain eligible will be randomly assigned in double blinded fashion in a 1:1 ratio to receive either phentermine 15.0 mg or placebo, combined with an additional 24 weeks of BT. They will then meet with trained research staff who will instruct them in the use of the study medication and provide the first month's supply of medication.

All subjects will then complete an outcome assessment, as described below.

7.3 Outcome Assessments

All subjects will be asked to attend 3 outcome assessments, which will occur at baseline (week -5,), randomization (week 0) and week 24. These assessments will include an evaluation of potential predictors of weight loss and assessment of the primary outcome measures used to judge the effectiveness of the treatments in inducing weight loss (described below). BT responders (who do not participate in the randomized trial) will provide weight, CVD, and questionnaire outcome measures at week 24, but will not be asked to complete the other portions of the in-person assessment at that time.

Each in-person outcome assessment visit will take approximately 2 hours. Subjects will be asked to fast for 8 hours prior to the in-person visit (overnight fast). Questionnaire measures will be completed online within 2 weeks of the in-person visit. A paper version of these measures will be provided to subjects upon request.

7.4 Treatment Visits

As described above, subjects will attend 4 initial, once weekly, 20-30 minute, individual BT sessions ("BT run-in;" week -4 to week -1). The first BT session will be scheduled immediately following the baseline outcome assessment. After completing the randomization visit (week 0), all subjects will continue to attend

BT sessions, provided in the same treatment format, weekly for the first 12 weeks (12 sessions) and every-other-week for the last 12 weeks (6 sessions).

7.5 Missed Visits

Subjects who miss a treatment visit will be contacted by the research coordinator and invited to complete a make-up session with study staff, in person or by phone (except for visits at which medication is distributed). Subjects who do not attend a randomization visit within 2 weeks of the end of the BT run-in will not be eligible to continue participation in the study. All subjects who complete a randomization visit will be invited to complete the week 24 assessment, even if they have discontinued the study medication or attendance of BT visits.

7.6 Subject Withdrawal

A subject may voluntarily withdraw from the study at any time for any reason. The investigator or sponsor also may withdraw the subject from further participation at any time, if it is considered in the best interest of the subject or the study, without prejudice to the subject's future medical care. It will be documented whether or not each subject completes the clinical study.

The primary reason for a subject's premature discontinuation from the study will be selected from the following standard categories and documented in the source documents:

Adverse event (AE): One or more clinical or laboratory events which, in the medical judgment of the investigator, are grounds for discontinuation, even if the event does not appear to be related to study drug. The subject may withdraw because of an AE even if the investigator does not feel that it is grounds for discontinuation. This category includes subject death.

Withdrawal of consent: The subject desires to withdraw from further participation in the study.

Lost to follow-up: In the case of subjects who do not return to the center for study procedures and cannot be contacted, study personnel will make vigorous and repeated attempts (minimum of 3) to contact the subject. If all attempts to contact the subject fail, that subject will be considered to be lost to follow-up and discontinued from the study.

Protocol violation: The subject's laboratory or other findings or conduct fail to meet the protocol entry criteria or fail to adhere to the protocol requirements.

Subject pregnancy or intention of becoming pregnant

The **Stopping Criteria** for individual subjects include:

1. The Principal Investigator and/or Medical Monitor conclude it is unsafe for the subject to continue.
2. A new diagnosis is made of a significant medical condition which could influence the response to phentermine (e.g., congestive heart failure).
3. A medication is begun that could alter the subject's responses to phentermine.

Subjects meeting individual stopping criteria will be withdrawn from the trial.

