7.7 Early Termination Visits

Whenever possible, subjects who withdraw early or who are asked by the investigator to cease participation in the study will have one final visit to collect study medication and to follow up regarding adverse events.

8 Study Evaluations and Measurements

The following measures will be collected during all outcome assessments, unless otherwise specified.

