Phase 2: Primary analyses will be based on the all-randomized population. The null hypothesis being tested is that there will be no significant difference between non-responders assigned to BT+M and BT+P in mean percentage of initial weight lost at 24 weeks post-randomization. To assess the primary phase 2 outcome of percent weight change by treatment group (among non-responders), a mixed effects model will be fit with treatment group (BT+P, BT+M) as a between-subjects factor and time (week) as a within-subjects factor. We will use the group x time interaction to estimate and test treatment group differences at week 24 (primary endpoint). In fitting the mixed effects model with residual maximum likelihood, a variance-covariance structure will be selected based on criteria such as the Akaike's Information Criterion (AIC). The results from the mixed model will be summarized by mean (SE) for each treatment group at week 24. Secondary analyses comparing IBT+M and IBT+P in changes in hunger, satiety, reinforcing efficacy of food, and impulsivity from randomization to week 24 will be conducted using similar analytic strategies, as will exploratory analyses of change in cardiometabolic risk factors, quality of life, and depression. Similar mixed effects models also will be used to compare differences in percent weight loss from randomization to week 24 between early non-responders treated with BT+M and early responders who attend a randomization visit and are treated with BT alone. Logistic regression will be used to examine differences between BT+M and BT+P in percent of subjects who achieve a post-randomization loss of $\geq 5\%$ and $\geq 10\%$ of initial body weight at week 24. Subjects who do not provide a week 24 weight will be considered as not having achieved the categorical weight loss.

9.2.1 Missing Data.

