All analyses will be conducted using the ITT principle, in which all available data on all randomized patients are included. This approach minimizes bias if subjects drop out of the intervention for different reasons. Assuming adequate fit of the mixed effects models to the data, the proposed nested random effects models are the most robust to missing data assumptions among standard longitudinal models that analyze all subjects regardless of how many post-randomization visits are missed.¹¹¹ The following missing or unbalanced data scenarios can be accommodated by such models: attrition (drop out), missed interim visits, and missing covariate data where a subject is interviewed but data are missing on covariates of interest. All three types of missing data are handled by way of maximum likelihood under the proposed mixed effects models and the missing at random assumption (MAR). Therefore, we will explore the potential bias of missing data by comparing completers and non-completers to see if they differ systematically on values of non-missing variables. There are many ways to assess the assumption of MAR. We will consider imputing missing endpoint data using multiple imputation techniques, fitting selection models (e.g. MNAR), and fitting pattern mixture models. Sensitivity analyses, including an analysis of the protocol-compliant population, also will be conducted.

Participants' data will be excluded from analyses in the event of pregnancy, amputation, bariatric surgery, or death. Any data collected following such events will be treated as missing, using the analytic methods described above. Additional criteria associated with subject censorship will be considered prior to initiating recruitment.

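### Section 7.6 takes subjects who meet a stopping criterion out of the trial, which conflicts with the week-24 follow-up offered in 7.5 and can lose primary-endpoint weights for drug-related reasons

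*Combined protocol and SAP*

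**What the plan says.** Protocol section 7.6 lists three individual stopping criteria:

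- the principal investigator and/or medical monitor "conclude it is unsafe for the subject to continue";
- "A new diagnosis is made of a significant medical condition which could influence the response to phentermine";
- "A medication is begun that could alter" the subject's response to phentermine.

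The consequence is mandatory: "Subjects meeting individual stopping criteria will be withdrawn from the trial".

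Section 7.7 says that, where possible, subjects who leave early "will have one final visit to collect study medication and to follow up regarding adverse events". It does not mention a week-24 weight.

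Section 7.5 says: "All subjects who complete a randomization visit will be invited to complete the week 24 assessment, even if they have discontinued the study medication". The sentence goes on to cover subjects who no longer attend BT visits.

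Two other sections separate stopping the drug from leaving the study. Section 5.3 keeps subjects whose capsules are terminated in BT to week 24. Section 13.1.1 lets the investigator or physician withdraw a subject from the medication alone.

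On analysis, 9.2.1 describes ITT as an approach "in which all available data on all randomized patients are included", with missing values handled by maximum likelihood under MAR. It names pregnancy, amputation, bariatric surgery and death as the events after which data are not used. For the responder endpoints, 9.2 says: "Subjects who do not provide a week 24 weight will be considered as not having achieved the categorical weight loss".

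**The concern.** A subject who, for example, starts a medication that could alter the response to phentermine is withdrawn from the trial under 7.6 but invited to week 24 under 7.5. Site staff have no rule for choosing between the two.

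The missing weights would not be a random subset. Two of the three criteria are defined by response to phentermine. The first can plausibly be triggered by drug effects listed in 13.1, such as raised blood pressure, palpitations or tachycardia. Withdrawals could therefore be more frequent on BT+M.

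The mixed model would in effect predict a withdrawn subject's week-24 weight from subjects in the same arm who stayed. If withdrawn subjects lose less weight than that, the treatment difference is overstated. The responder analyses treat the same subjects as failures, which can only lower the success rate in their arm. A data-collection rule would thus move the primary and responder results in different directions.

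**Working it through.** **1. The passages side by side**

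| Section | What ends | Week-24 weight sought? |
|---|---|---|
| 5.3 | Study capsules; BT continues to week 24 | Not stated here; 7.5 applies |
| 13.1.1 | Medication only; BT may be completed unless weight loss is contraindicated | Not stated here; 7.5 applies |
| 7.5 | Medication or BT attendance | Yes, for all who complete a randomization visit |
| 7.6 | Trial participation | No provision |
| 7.7 | Early termination | No; one visit for medication return and adverse events |
| 9.2.1 | Use of data after four named events | The 7.6 criteria are not among the four |

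The analysis plan therefore has no reason to discard week-24 weights from subjects who meet a 7.6 criterion, but 7.6 and 7.7 do not provide for collecting them.

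**2. Inputs (section 9.1)**

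Mean week-24 loss is 6.5% on BT+M and 2.0% on BT+P, a difference of 4.5. The SD is 5.5, so d = 4.5/5.5 = 0.818. There are 25 subjects per arm with 20% attrition, so 25 × 0.8 = 20 completers per arm. Alpha is .05, and 9.2 specifies two-tailed tests.

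**3. The plan's own power figure**

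Power is from the noncentral t distribution with df = n1 + n2 − 2 and noncentrality d × √(n1·n2/(n1 + n2)). For 20 against 20 the noncentrality is 0.818 × √10 = 2.587.

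- One-sided: 81.5%, the stated figure.
- Two-sided: 71.3%.

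The gap between these is a question of sidedness and has nothing to do with 7.6. The two-sided value is used below only as a reference point.

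**4. Possible bias in the primary comparison**

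The documents give no rate of stopping-criterion withdrawals. Assumptions: k of 25 BT+M subjects are withdrawn; the model in effect assigns them the arm mean of 6.5%; their true week-24 loss is the BT+P mean of 2.0%; interim weights do not inform the prediction.

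Overstatement = (k/25) × (6.5 − 2.0)

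| k | Share | Overstatement (points) | True difference |
|---|---|---|---|
| 1 | 4% | 0.04 × 4.5 = 0.18 | 4.32 |
| 2 | 8% | 0.08 × 4.5 = 0.36 | 4.14 |
| 3 | 12% | 0.12 × 4.5 = 0.54 | 3.96 |

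Under that 2.0% assumption these are upper values, because interim weights would reduce them.

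**5. Responder analyses**

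Counting a withdrawn subject as a failure costs 1/25 = 4 percentage points only if that subject would otherwise have succeeded. Under the step 4 assumption (mean 2.0, SD 5.5, normality assumed):

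- P(loss ≥ 5%) = P(Z ≥ 3.0/5.5 = 0.545) = 0.29, so the expected cost is 4 × 0.29 ≈ 1.2 points.
- P(loss ≥ 10%) = P(Z ≥ 8.0/5.5 = 1.455) = 0.07, so the expected cost is 4 × 0.07 ≈ 0.3 points.

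**6. Power**

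If the losses fall within the planned 20% attrition, power does not change. If they come on top of it and only in BT+M, two-sided power is:

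- 20 against 20: 71.3%
- 20 against 18 (noncentrality 0.818 × √(360/38) = 2.518): 68.8%
- 20 against 17 (noncentrality 0.818 × √(340/37) = 2.480): 67.4%

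**The case against.** The strongest reply is that 7.5 governs treatment discontinuation and 7.6 governs study withdrawal, so the two do not meet. That reading is possible, but no section states it. 7.5 covers all subjects who complete a randomization visit without exception, and two of the 7.6 criteria concern response to treatment rather than any reason to stop weighing someone.

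Several narrower replies stand and limit the point:

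- Ordinary drug intolerance goes through 5.3 and 13.1.1, which leave 7.5 in force. Only subjects who meet a 7.6 criterion are exposed.
- Section 8.1 calls for a weight at all clinic visits, so a final clinic visit under 7.7 should already yield one. It would not be a week-24 weight.
- Interim weights may inform the model, and 9.2.1 commits to sensitivity analyses, with multiple imputation, selection and pattern-mixture models to be considered. These soften the problem but do not replace the missing endpoint.

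A reader might also infer more than the documents support:

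- **That 7.6 breaches ITT.** Section 7.5 does not mention ITT. The promise in 9.2.1 concerns available data, and a withdrawal reduces what is available without breaking it.
- **That every protocol violator is withdrawn.** In 7.6 protocol violation is a recorded reason for discontinuation. Mandatory withdrawal attaches only to the three stopping criteria.
- **That the responder result loses a full 4 points per withdrawal, or that power falls to around 61–66%.** The first holds only for subjects who would have succeeded. The second requires removing 2 to 4 subjects from both arms, which does not match a drug-related excess in one arm.

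**Conclusion.** The conflict between 7.5 and 7.6 is real and should be resolved, because it decides whether the primary-endpoint weight is sought for a group whose withdrawal may be related to treatment.

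Its size is modest and uncertain. With 1 to 3 of 25 BT+M subjects withdrawn, the planned 4.5-point difference would be overstated by up to about 0.18 to 0.54 points. That rests on three assumptions not found in the documents: the number withdrawn, a true loss at the BT+P mean, and no help from interim weights. The opposing effect on the responder endpoints is small in expectation under the same assumptions. With 2 to 3 BT+M losses beyond the planned attrition, two-sided power falls from 71.3% to between 68.8% and 67.4%; within the planned attrition it does not change.

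Drug-related imbalance in withdrawals is a plausible risk. The documents do not show that it will occur.

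**What to change.** Reconcile 7.5, 7.6 and 7.7, together with 5.3 and 13.1.1, by separating the end of treatment from the end of outcome follow-up. State in 7.6 that meeting a stopping criterion does not by itself end follow-up: the subject stays in the all-randomized population and is invited for the week-24 weight as 7.5 already provides, unless consent is withdrawn, the subject is lost to follow-up, or one of the 9.2.1 exclusion events occurs. In 7.7, say that the final visit does not replace that invitation.

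The stopping criteria themselves, and which treatment stops and when, remain with the investigators and are not part of this change.

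The cost is a short wording amendment and a few additional week-24 weigh-ins.
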